Stroke is a leading cause of long-term disability worldwide, often resulting in cognitive impairments, particularly in attention, which can significantly affect patients' quality of life and daily functioning. Evidence suggests that music therapy can enhance cognitive recovery during neurorehabilitation by engaging multiple brain networks and promoting neuroplasticity. While home-based rehabilitation has demonstrated effectiveness post stroke, there is limited evidence regarding the feasibility and impact of music therapy delivered at home for stable stroke patients. Furthermore, no studies have examined the efficacy of structured music therapy as part of a cognitive rehabilitation program in Malaysia, despite efforts over the past decade to promote music for therapeutic purposes. Unlike in other countries where music therapy is an established neurorehabilitation modality, it has not been formally incorporated into most local neurorehabilitation programs. This study proposes to investigate the effects of home-based music therapy on cognitive functions in stroke patients in Malaysian setting. If successful, this approach could support the integration of music therapy into clinical neurorehabilitation home-based settings, promoting its wider use for cognitive recovery post-stroke.

OBJECTIVES/OUTCOMES**Objectives:**

1. To determine the feasibility and acceptability of a structured home-based music therapy rehabilitation programme for improving attention and processing speed among stable stroke survivors in Malaysia, as measured by recruitment rate, adherence, retention, and participant satisfaction.
2. To explore the preliminary effects of the home-based music therapy rehabilitation programme on attention and processing speed in post-stroke patients using standardized cognitive outcome measures.
3. To assess the safety and practicality of implementing a home-based music therapy rehabilitation intervention, including monitoring adverse events, caregiver involvement, and compliance with the prescribed programme.

Expected outcomes:**1. Feasibility and Acceptability**

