It is expected that the home-based music therapy rehabilitation programme will demonstrate acceptable feasibility among stable stroke survivors in Malaysia. This includes achieving satisfactory recruitment and retention rates, good adherence to the prescribed intervention, and positive participant-reported satisfaction. These outcomes will indicate that the programme is acceptable and practicable for implementation in a home setting within the local context.

2. Preliminary Cognitive Outcomes

The study is expected to show trends toward improvement in attention and processing speed following participation in the home-based music therapy rehabilitation programme, as measured by standardized cognitive assessment tools. While the study is not powered to determine definitive efficacy, the findings will provide preliminary data on potential cognitive benefits and inform the selection of outcome measures and effect size estimates for future larger-scale trials.

3. Safety and Practicality

The intervention is expected to be safe, with minimal or no adverse events related to participation. It is anticipated that participants and caregivers will be able to implement the programme with minimal difficulty, demonstrating adequate compliance with the prescribed activities. These findings will support the practicality of delivering a structured music therapy rehabilitation intervention in a home-based setting.

METHODOLOGY

Study design

This study will adopt a prospective, single-centre, randomized controlled feasibility study design with two parallel groups: an intervention group receiving music therapy in addition to standard neurorehabilitation, and a control group receiving only standard neurorehabilitation. The primary focus is to evaluate the feasibility, acceptability, and safety of a structured home-based musical rehabilitation programme for cognitive rehabilitation after stroke. Secondary objectives include exploration of preliminary effects on attention and processing speed.

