Each session begins with 3–5 minutes of focused listening, during which participants will be instructed to observe and listen attentively to the musical compositions generated by the Finale music software. The software's user-friendly interface will display a tempo line adorned with pertinent remarks and symbols, providing clear guidance for the patients to follow.

An Eight-Tone Desk Bell (Figure 1) will be integrated with the Finale music software (Figure 2), enabling stroke patients to observe and listen to musical compositions generated.

6. Rhythm–Action Training

Participants will actively engage with the music and synchronise tapping on an Eight-Tone Desk Bell. The rhythmic and visual cues will be displayed on the Finale software interface, targeting processing speed, sustained attention, and sensorimotor integration.

7. Session Dosage and Frequency

Each session lasts 40 minutes and is conducted daily for five days per week, in accordance with rehabilitation literature. Session duration and frequency are recorded in the caregiver checklist.

8. Progress Monitoring and Adjustment

Progression is guided by bi-weekly level assessments by the music therapist at their homes. Adjustments made based on participant performance and endurance on the songs chosen earlier. The adjustments will include either changing the song within the same difficulty level or change to the songs in the next level of difficulty.

9. Adherence Monitoring

Caregivers will complete the checklist after each session, documenting completion, duration, participant alertness, and signs of fatigue. Weekly therapist phone call follow-ups support adherence and address concerns.

Control Group: Standard Care

Participants in the control group continue with usual standard neurorehabilitation program as prescribed by the rehabilitation team, without exposure to the music-based intervention.

This will provide a baseline to compare outcomes with the intervention group and evaluate the feasibility and preliminary effects of the music therapy intervention. The usual cognitive rehabilitation program during the subacute stroke period focuses on restoring cognitive abilities

such as attention, memory, executive functions, and communication. The key components typically include:

1. **Attention Training:** Exercises that improve sustained, selective, and divided attention, crucial for regaining concentration in daily activities.

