2. **Memory Aids:** Tools like mnemonic strategies, repetition tasks, and external memory aids (e.g., calendars, notes) help rebuild short-term and working memory.
3. **Executive Function Training:** Targeting skills such as problem-solving, planning, and organizing tasks through structured exercises, gradually improving independent thinking.
4. **Communication and Language Therapy:** Speech-language pathologists work with patients to improve verbal and non-verbal communication, focusing on both comprehension and expression.
5. **Problem-Solving Exercises:** These help patients break down real-life problems into smaller, manageable steps, encouraging better decision-making skills.

Both the intervention and control groups will continue receiving the standard care

Figure 1. Eight-Tone Desk Bell

[figure not shown]

Figure 2: Finale Music Software User Interface

Inclusion Criteria:

1. Diagnosed with ischemic or haemorrhagic stroke confirmed by CT scan
2. Duration of stroke within the first one year
3. Age 18 – 70 years old
4. Ability to provide informed consent
5. Understands Bahasa Melayu or English with basic communication abilities to follow instructions during therapy sessions
6. Mild to moderate cognitive impairments with MoCA score of 10-25, with incomplete score for the attention sections
7. Availability of caregiver (formal or informal) who can assist in the music therapy, monitor and give feedback during the music therapy sessions at home
8. Have one normal functioning hand to perform the movements during the music therapy rehabilitation program
9. Have good balance and able to sit upright

Exclusion Criteria:

1. Severe aphasia
2. Significant uncorrected hearing or visual impairments preventing engagement in music therapy.
3. Severe or unstable medical conditions (e.g., uncontrolled hypertension or diabetes).
4. Medications that significantly impair cognition or motor function (e.g., high-dose sedatives).
5. History of neurological diseases other than stroke (eg, Parkinson's disease).

Outcome measures

This will be assessed at baseline, after completion of 4-week sessions and also at 3 months after completion. Primary outcome measures are Montreal Cognitive Assessment (MoCA), Trail Making Test (TMT A and B), Digit Span (Forward and Backward) and Clock Drawing Test (CDT). The secondary outcome measure is computer-based Cogniplus software for Reaction Time and Attention tests

Sample size calculation:

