A sample of 40 subacute stroke patients (18 control and 18 intervention) within the first one year post-stroke, will be recruited from UMMC. This number is chosen based on practical considerations to evaluate feasibility metrics and exploratory analysis as in the objectives. For these purposes, a sample size of 36 is typically adequate to gather enough information about the practical aspects of the trial. This number could also ensure that the feasibility objectives are met even with at least 20% dropouts. This total number of 36 will be sufficient within the study period and the grant duration.

Statistical Analysis:

Descriptive Statistics and Exploratory Inferential Statistics will be used in this study.

The means, standard deviations, and 95% confidence intervals (CIs) for cognitive outcome measures (e.g., memory, attention, executive function scores) at baseline, post-intervention, and follow-up will be used. This will provide a preliminary understanding of the data distribution and effect sizes.

For the exploratory Inferential Statistics, independent t-test (or Mann-Whitney U Test) will be used to compare the mean changes in cognitive scores between the intervention and control groups. The independent t-test if the data are normally distributed. If not, we will use the Mann-Whitney U test as a non-parametric alternative.

Within each group, we will compare the baseline and post-intervention scores using the paired t-test for normally distributed data or the Wilcoxon signed-rank test for non-parametric data. Cohen's d will be used for independent t-tests (between groups) or r for non-parametric tests.

A repeated measures ANOVA (if the data is normally distributed) or a mixed-effects model will be used to explore changes over time (baseline, post-intervention, and follow-up). Given the small sample size, these analyses will likely be underpowered but can provide estimates of variability and preliminary trends.

RESEARCH DATA

Where will the data be kept?

The demographic data of the patients, and data on cognitive performance and other relevant data will be kept in a dedicated research file and hard drive. The files are in the laptop will be secured with password and the notes will be kept in a locker in the Department of Rehabilitation Medicine, Faculty of Medicine with one of the co-researchers.

Anonymity of data

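### The stated primary focus is feasibility, acceptability and safety, but only cognitive tests are named as outcomes and analysed, and the feasibility metrics have no numeric success criterion

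*Protocol*

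**What the plan says.** The Protocol ranks its questions in two incompatible ways.

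- **Objectives.** Objective 1 is feasibility and acceptability, "as measured by recruitment rate, adherence, retention, and participant satisfaction". Objective 3 is safety and practicality, "including monitoring adverse events, caregiver involvement, and compliance with the prescribed programme". Cognitive effects are objective 2 and are to be explored.
- **Study design.** "The primary focus is to evaluate the feasibility, acceptability, and safety of a structured home-based musical rehabilitation programme for cognitive rehabilitation after stroke". The next sentence reads: "Secondary objectives include exploration of preliminary effects on attention and processing speed".
- **Expected outcomes.** Recruitment and retention should be *satisfactory*, adherence *good* and satisfaction *positive*. The same section says the study is not powered for definitive efficacy.
- **Outcome measures.** "Primary outcome measures are Montreal Cognitive Assessment (MoCA), Trail Making Test (TMT A and B"), then Digit Span forward and backward and the Clock Drawing Test. The only secondary outcome is a computerised reaction-time and attention test.
- **Sample size calculation.** The number is justified on practical grounds, to serve feasibility metrics and exploratory analysis.
- **Statistical Analysis.** The descriptive part is "The means, standard deviations, and 95% confidence intervals (CIs) for cognitive outcome measures (e.g., memory, attention, executive function scores"). Comparisons between groups, within groups and over time follow, all on these scores.
- **Adherence Monitoring (intervention group, item 9).** "Caregivers will complete the checklist after each session, documenting completion, duration, participant alertness, and signs of fatigue". Weekly therapist calls are added. Item 4 gives the same checklist a safety-monitoring role.

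**The concern.** A feasibility trial is judged by whether its feasibility questions are answered against criteria fixed in advance. Here those questions lead the design and justify the sample size, then disappear when outcomes are listed and analysed. A team following Outcome measures and Statistical Analysis to the letter would report, as its primary result, efficacy comparisons that the Protocol itself calls underpowered. Feasibility would be left to narrative.

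Two things are at stake. First, with no number attached to *satisfactory* or *good*, almost any retention or adherence figure could be called acceptable afterwards. Second, labelling the cognitive tests primary invites readers to treat a chance finding, or a null one, as the trial's answer.

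**Working it through.** **1. The two rankings side by side**

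| Item | Objectives / Study design | Outcome measures | Statistical Analysis |
|---|---|---|---|
| Recruitment, retention, adherence | primary focus | absent | absent |
| Satisfaction | primary focus | absent | absent |
| Adverse events | primary focus (safety) | absent | absent |
| MoCA, TMT, Digit Span, Clock Drawing | secondary | primary | analysed |
| Computerised reaction time and attention | secondary | secondary | analysed |

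The rankings cannot both stand. A separate analysis plan could not settle the matter: it would have to contradict either Study design or Outcome measures.

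**2. What data the Protocol would yield**

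- Recruitment: screening and approach of eligible patients are described, so counts are obtainable.
- Retention: follows from attendance at the 4-week and 3-month assessments.
- Adherence: the checklist records completion and duration. Five sessions a week for four weeks gives 5 × 4 = 20 scheduled sessions.
- Satisfaction: no instrument and no time point.
- Adverse events: a general safety role for the checklist, whose listed fields are completion, duration, alertness and fatigue, plus weekly calls. Both are described only under the intervention group.

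**3. Precision available**

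The Protocol gives no precision target, so there is no figure to reproduce. The rate of 80% is an assumption. The 40 participants and 20 per arm come from the randomisation text; Sample size calculation also states 18 + 18 = 36.

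Wilson 95% interval: [p + z²/2n ± z√(p(1−p)/n + z²/4n²)] / (1 + z²/n), with z = 1.96.

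- Retention 32/40: (0.8480 ± 0.1329)/1.0960 = 65.2% to 89.5%.
- Adherent participants 16/20: (0.8960 ± 0.1999)/1.1921 = 58.4% to 91.9%. This treats each participant as adherent or not, so it presupposes a cut-off on the 20 sessions, which the Protocol does not give.
- Exact intervals are a little wider: 32/40, 64.4% to 90.9%; 16/20, 56.3% to 94.3%. With the smaller numbers: 29/36, 64.0% to 91.8%; 14/18, 52.4% to 93.6%.
- Zero events, two-sided 95% upper limit 1 − 0.025^(1/n): 16.8% for n = 20 and 18.5% for n = 18.

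**4. Power for the tests labelled primary**

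The approximation is Φ(d√(n/2) − 1.96), with two-sided alpha 0.05 assumed and 18 to 20 per arm. At standardised effects of 0.3, 0.5 and 0.8, power is about 15–16%, 32–35% and 67–72%. This agrees with the Protocol's own statement that it is not powered for efficacy.

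**The case against.** The strongest reply is that feasibility is not neglected. Objectives 1 and 3 name the measures, the sample size is tied to them, and most of the data would exist: attendance gives retention, the checklist gives adherence, and screening gives recruitment. That stands. A reader might infer that the trial has no feasibility endpoint at all, or could not say whether the programme is feasible. The Protocol does not support that. The faults are in ranking, definition and criterion, and for satisfaction also in collection.

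A reader might also infer that adverse events are not collected, or only in one arm, so that harms could never be attributed to the programme. That too goes further than the text. The checklist has a safety-monitoring role, therapists call weekly and assess at home every two weeks, and caregivers are to monitor and give feedback. Nothing explicitly confines adverse-event monitoring to the intervention arm, and expected safety is framed as events related to participation. What remains is that no adverse-event item is specified and no route is described for controls.

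Finally, analysis detail may properly sit in a statistical analysis plan that is not shown. So the absence of, say, a formula for a retention interval is not the complaint. The contradiction over what is primary is in the Protocol and must be resolved there.

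**Conclusion.** The concern holds in this form: the Protocol contradicts itself on what is primary. None of the four metrics in objective 1, and no adverse-event measure from objective 3, reaches the outcome list, and success has no numeric criterion. This must be corrected before enrolment, because criteria chosen after the data are seen carry little weight.

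The conclusion rests on the text, not on a calculation. The figures only show why criteria matter: at an assumed 80%, retention in 40 is known to about ±12 points and the proportion adherent in 20 to about ±17 points, slightly worse with arms of 18. Even an event-free intervention arm of 20 is compatible with a true rate of up to about 17%.

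**What to change.** In Outcome measures:

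1. Name as primary: recruitment; retention at 4 weeks and at 3 months; adherence (sessions completed out of 20 scheduled, with a stated cut-off for an adherent participant); satisfaction, with a named item and time point; and adverse events.
2. Relabel all cognitive tests, including the computerised one, as secondary and exploratory.
3. Before first enrolment, set numeric progression criteria of the sponsor's choosing. Say whether each applies to the observed proportion or to a confidence limit, and report proportions with 95% confidence intervals.
4. Record adverse events with the same question in both arms. Have someone already on the study team, other than the blinded assessor, collect satisfaction and adverse events, since the answers could reveal allocation.

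The cost is a protocol amendment with a matching registry entry, and two short items at visits already planned. The real downside is that the sponsor commits in advance to criteria it may miss.

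### The outcome ranking does not follow the objectives: only cognitive tests are primary in a feasibility study, the named attention and reaction-time test is secondary, and no lead cognitive score or visit is fixed

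*Protocol*

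**What the plan says.** **Aims.** Under Study design the protocol states: "The primary focus is to evaluate the feasibility, acceptability, and safety of a structured home-based musical rehabilitation programme". It then adds: "Secondary objectives include exploration of preliminary effects on attention and processing speed". Objective 1 measures feasibility and acceptability by recruitment rate, adherence, retention and satisfaction. Objective 2 is the cognitive one: "To explore the preliminary effects of the home-based music therapy rehabilitation programme on attention and processing speed in post-stroke patients".

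**Outcome ranking.** Under Outcome measures: "Primary outcome measures are Montreal Cognitive Assessment (MoCA), Trail Making Test (TMT A and B), Digit Span (Forward and Backward) and Clock Drawing Test (CDT"). Below these it places the computerised test: "The secondary outcome measure is computer-based Cogniplus software for Reaction Time and Attention tests". On timing: "This will be assessed at baseline, after completion of 4-week sessions and also at 3 months after completion".

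**Analysis.** Statistical Analysis describes the outcomes as "cognitive outcome measures (e.g., memory, attention, executive function scores"). It compares mean changes between groups without naming a visit, compares baseline with post-intervention within each group, and explores all three time points with a repeated measures ANOVA or a mixed model. It calls the inference exploratory and likely underpowered.

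**Use of the results.** Expected outcomes (item 2) says the study is not powered for definitive efficacy. It also says the findings will inform which outcome measures and which effect sizes are used in later, larger trials.

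**The concern.** The ranking departs from the objectives at two levels. First, the study is primarily about feasibility, yet no primary outcome is a feasibility measure. Second, the cognitive aim is limited to attention and processing speed. The primary list nevertheless contains a global screen and a clock-drawing test, and the only instrument the protocol itself describes as testing attention and reaction time is secondary. The examples in Statistical Analysis move further away: memory and executive function appear in no objective, and processing speed is not mentioned.

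No score or visit is marked as the one that answers Objective 2. Any of the primary scores, at either visit, could therefore be reported as the preliminary effect. Since these results are meant to guide the choice of outcome and effect size for the next trial, a favourable chance result could be carried forward as a planning value.

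**Working it through.** The protocol gives no alpha, power or effect size, so there is no stated figure to reproduce. The check sets the sections against each other, counts the available comparisons, and shows what that count implies under stated assumptions.

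**1. Ranking against aims**

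| Item | Standing in Study design and Objectives | Standing in Outcome measures |
|---|---|---|
| Recruitment, adherence, retention, satisfaction | Primary focus | Not listed |
| Attention and processing speed | Secondary, exploratory | Trail Making and Digit Span primary; Cogniplus secondary |
| Global cognition (MoCA), clock drawing | Not an objective | Primary |

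The protocol does not map tests to domains. Placing Trail Making and Digit Span under speed and attention rests on their common use.

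**2. Count**

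- Primary scores: MoCA, TMT-A, TMT-B, Digit Span Forward, Digit Span Backward, CDT = 6.
- Post-baseline visits: end of the 4 weeks, and 3 months after completion = 2.
- Available between-group comparisons: 6 × 2 = 12.

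Twelve is an inference, because the between-group test names no visit. If it is used at one visit only, the count is 6. Cogniplus is left out because the protocol does not say how many scores it yields.

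**3. Chance of at least one false positive**

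Assumption: two-sided 0.05 per test and no true effect.

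- Independent tests: 1 − 0.95^m. For m = 6, 1 − 0.95^6 = 0.265. For m = 12, 1 − 0.95^12 = 0.460.
- Correlated tests: simulation of m equally correlated normal test statistics (300,000 draws), counting draws in which any |z| exceeds 1.96.

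| Correlation (assumed) | 6 comparisons | 12 comparisons |
|---|---|---|
| 0 | 26% | 46% |
| 0.3 | 24% | 40% |
| 0.5 | 21% | 32% |
| 0.7 | 16% | 23% |
| 0.9 | 11% | 14% |

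With one lead score at one visit, the figure for that comparison is 5%.

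**4. Effect size that selection alone would produce**

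This bears more directly on the protocol's stated use of the results. With n per arm, a standardised difference has standard error of about √(2/n). Multiplying by the simulated mean of the largest z among 12 null comparisons gives the expected size of the best-looking result. The protocol gives both 18 and 20 per group, so both are shown.

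| Correlation (assumed) | Mean largest z | n = 18: × √(2/18) = 0.333 | n = 20: × √(2/20) = 0.316 |
|---|---|---|---|
| 0 | 1.63 | 0.54 | 0.52 |
| 0.5 | 1.15 | 0.38 | 0.36 |
| 0.7 | 0.89 | 0.30 | 0.28 |
| 0.9 | 0.52 | 0.17 | 0.16 |

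If the best of 12 were chosen and there were no effect at all, the next trial would on average be handed a standardised difference of about 0.2 to 0.5.

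**The case against.** The strongest reply is that the cognitive analysis is openly exploratory. The protocol states no alpha, claims no significance and says the study is not powered for efficacy. Family-wise error is a confirmatory yardstick, and multiplicity among exploratory outcomes is commonly left to a statistical analysis plan, which is not shown here. This stands: no formal adjustment is required, and the percentages only illustrate a risk.

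Three stronger readings are tempting, and the protocol does not support them.

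- *A reader might infer that the primary list misses the cognitive objective altogether.* It does not. Four of the six scores (TMT-A, TMT-B, and the two in "Digit Span (Forward and Backward) and Clock Drawing Test (CDT")) plausibly address attention or speed. Inclusion criterion 6 also ties MoCA to attention through its attention sections. The list is mixed.
- *A reader might infer that 12 or more primary tests are planned.* The protocol says only that the scores are assessed at both visits. A higher count would require assuming a number of Cogniplus scores.
- *A reader might infer that the sponsor intends to carry forward the largest effect.* Nothing says so, and trying several instruments fits a feasibility study. The point is that the text does not prevent such a choice.

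It is also fair to say that the memory and executive-function wording is only an illustrative list and excludes nothing. That part is a matter of consistency.

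The reply does not reach the ranking itself. The protocol, not a later plan, fixes which outcomes are primary, and that ranking conflicts with its own Study design section.

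**Conclusion.** The concern holds in a limited form. The outcome ranking contradicts the stated aims: no primary outcome measures feasibility, the primary cognitive list is only partly on target, and the instrument labelled for attention and reaction time ranks below a global screen and clock drawing. No lead score or visit is named for the cognitive objective.

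With up to 12 available comparisons, the chance of at least one false positive is 46% if independent, about 32% at correlation 0.5 and 23% at 0.7. If only one visit is compared, the corresponding figures are 26%, 21% and 16%. These rest on an assumed two-sided 0.05, no true effect, equal correlation, and the inference that either visit could be used. They describe the room for selective emphasis in the effect size passed to the next trial, not a breach of a confirmatory error rate. The change should be made; it does not put the conduct of the study in doubt.

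**What to change.** 1. In Outcome measures, make the feasibility and acceptability measures of Objective 1 (recruitment, adherence, retention, satisfaction) primary. Relabel all cognitive tests as secondary and exploratory.
2. Before outcome data are seen, name one lead processing-speed score, one lead attention score and one lead visit. An example is TMT-A for speed and one prespecified Cogniplus or Digit Span score for attention, at the end of the 4 weeks. If Cogniplus is chosen, define the exact score, since the protocol names only the tests.
3. List the remaining tests, including MoCA and CDT, as supportive.
4. In Statistical Analysis, name the visit for the between-group comparison. Report every between-group difference with a 95% confidence interval and without significance claims, and align the outcome examples with attention and processing speed.

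**Cost.** This is a wording amendment. The cognitive tests are already planned and Objective 1 already names the feasibility measures, so participants carry no added burden. The sponsor gives up the freedom to choose the lead test after seeing the results.

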Patients with a history of stroke who are admitted to, or attending follow-up at, University Malaya Medical Centre (UMMC) during the study period will be screened for eligibility. Eligible patients will be approached and provided with detailed information about the study and invited to participate. In addition, public advertisements (posters and flyers within UMMC) will be used to increase awareness of the study and facilitate recruitment. Patients who meet the inclusion criteria and agree to participate will be enrolled only after providing written informed consent.

Following enrolment, all participants will be allocated to either an intervention group or a control group in a 1:1 ratio. To ensure that there are exactly 20 patients in both the control and intervention groups, block randomization will be used using a random number generator. After randomization, the group assignments will be kept in a password-protected file that only the study coordinator can access. The assessor will not have access to this information because the patients will be labelled with anonymous codes that do not reveal whether they are in the control or intervention group. The assessor will only know the code, not the group assignment, ensuring unbiased evaluation.

A certified music therapist will prescribe the intervention and train the patients and caregivers before the start of the home-based music therapy. A trained assessor will evaluate the cognition at baseline, and also the outcome. The assessor is blinded to the patients' allocation group and will evaluate the cognitive outcomes at baseline, immediately after completion of the intervention period at four weeks and at 3 months post intervention.

Intervention group

The music therapy session described follows a structured and engaging approach, aimed at enhancing the patient's cognitive skills. Here's a summary of the session components:

Intervention Group: Home-Based Music Therapy Rehabilitation Program

1. Song Materials and Levels

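### The protocol gives two conflicting sample sizes, 40 (20 per group) and 36 (18 per group), and its 20% dropout claim cannot be checked because no number needed after dropout is stated

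*Protocol*

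**What the plan says.** Two parts of the protocol's Methodology fix the sample size.

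- **Study design (allocation text).** Allocation is 1:1, and the number per group is explicit: "To ensure that there are exactly 20 patients in both the control and intervention groups, block randomization will be used". That is 40 in total.
- **Sample size calculation.** The opening sentence reads "A sample of 40 subacute stroke patients (18 control and 18 intervention) within the first one year post-stroke, will be recruited from UMMC". The section then says that "a sample size of 36 is typically adequate to gather enough information about the practical aspects of the trial" and closes with "This total number of 36 will be sufficient within the study period and the grant duration".

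The basis of the number is given as practical: "This number is chosen based on practical considerations to evaluate feasibility metrics and exploratory analysis as in the objectives". No power calculation is offered. On losses, the section says: "This number could also ensure that the feasibility objectives are met even with at least 20% dropouts". It does not say how many participants must remain for the objectives to be met, or whether 36 is a number enrolled or a number retained.

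**The concern.** The opening sentence of the sample size section contradicts itself, and its split of 18 and 18 contradicts the allocation text. These are figures in running prose, so a broken table cannot explain them, and the protocol contains no change log that would mark one of them as superseded.

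The number to be randomised is the most basic operational figure of a trial. A coordinator who follows the allocation text prepares a list of 20 and 20; a reader of the sample size section expects 18 and 18. Stopping at 36 departs from the first, and going on to 40 departs from the second. Whichever is done, the final report will have to explain a departure from the protocol that comes only from its wording.

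The dropout sentence adds to the difficulty. It is the only robustness claimed for the sample size, and no two stated figures are linked by a 20% loss. It also sets a minimum loss with no maximum, so read literally it covers any amount of dropout.

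**Working it through.** **Inputs, all from the protocol**

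- Headline total: 40 (Sample size calculation).
- Split in the same sentence: 18 and 18 (Sample size calculation).
- Number called adequate, and total restated: 36 and 36 (Sample size calculation).
- Per-group number: 20 and 20, at 1:1 (Study design).
- Dropout: 20% or more (Sample size calculation).
- Required number of completers: not stated. Alpha, power, effect size and standard deviation: not stated, so no power formula applies.

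**Step 1. Try to reproduce the stated total.** Total = sum of the groups.

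- 18 + 18 = 36. This does not reproduce 40; the difference is 4 patients, and 4/40 = 10%.
- 20 + 20 = 40. This agrees with the headline but not with the split or with either mention of 36.

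The stated figures therefore reduce to two totals: 40 (= 20 + 20) and 36 (= 18 + 18).

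**Step 2. Suppose 40 are recruited and 36 complete.** Implied loss = 1 − 36/40 = 10%. The paragraph speaks of 20% or more.

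**Step 3. Apply a 20% loss to each total.** Number left = N × (1 − 0.20).

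- From 40: 40 × 0.8 = 32, or 16 per group.
- From 36: 36 × 0.8 = 28.8, so about 28 to 29, or 14.4 per group.

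**Step 4. Suppose 36 is the number needed after a 20% loss.** Number to enrol = 36/(1 − 0.20) = 45. At 1:1 this is 18/0.8 = 22.5, rounded up to 23 per group, so 46. The incorrect but common inflation, 36 × 1.2 = 43.2, gives 44. None of these is a stated figure.

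**Step 5. Ask whether some unstated completer target would explain the printed totals.**

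- 32 completers: 32/0.8 = 40.
- 30 completers: 30 × 1.2 = 36 by the incorrect inflation; the correct one gives 30/0.8 = 37.5, so 38.

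Such targets could lie behind the totals, but the protocol states neither 30 nor 32. The 20% claim can be neither confirmed nor refuted from the text.

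**The case against.** The strongest defence is that 40 are to be recruited and 36 to be evaluable. The wording does not support it: the 18 and 18 are attached to patients who are to be recruited, and 36 is called the total that the study period and grant can carry. If the defence is accepted all the same, it gives a 10% allowance, not 20%.

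A second defence is that this is a feasibility study, with a number chosen on practical grounds and no claim of power. That stands: no power calculation is owed, and no stated decision threshold turns on 36 versus 40. It does not explain why two totals are given.

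Several stronger readings are tempting, and the documents do not support them.

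- **That the 20% tolerance is false, or fits none of the figures.** This requires 36 to be the number needed after dropout. The protocol never says so. The text can be read as 36 (or 40) enrolled, with a fifth lost and the result still acceptable.
- **That the trial would be 11% to 22% short of its evaluable number.** Those percentages are (36 − 32)/36 and (36 − 28)/36. They treat 36 as a stated completer target, and no such target is stated.
- **That a randomisation list cannot be built.** The allocation text alone, with 1:1 and 20 per group, is enough to build one. The fault is that the sample size section disagrees with it.
- **That a feasibility endpoint has lost its denominator.** The first objective lists recruitment rate, adherence, retention and satisfaction. Nothing makes the planned total the denominator of any of them.
- **That 40 is plainly right and costs nothing.** The only statement on resources covers 36.

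The dropout sentence is also hedged: it says the number could ensure the objectives, not that it will.

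**Conclusion.** The contradiction is real and must be resolved. The protocol plans for 40 (20 per group) and for 36 (18 per group), a gap of 4 patients or 10% of the larger total, and it contains nothing that decides between them. This part rests on addition alone.

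The dropout statement is unsupported rather than disproved. A 20% loss leaves 32 from 40 or about 28 to 29 from 36, and whether either is enough cannot be judged without a stated number of completers. The figure of 45 applies only on the assumption that 36 must remain after a 20% loss. Two faults in the sentence do not depend on that assumption: it gives no upper limit to the loss, and it suggests that a sample size can secure the feasibility objectives whatever the dropout, although retention is itself one of the feasibility measures.

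No single corrected total follows from the documents. The sponsor has to say which was intended.

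**What to change.** State one number to be randomised, one number per group and one expected number of completers at 20% loss, identical under Study design and Sample size calculation.

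- **If 40 is kept** (20 per group, as in the allocation text): replace the 18 and 18 split and both mentions of 36, state that 32 (16 per group) are expected after a 20% loss, and confirm that 40 fits the study period and the grant.
- **If 36 is intended:** replace the headline 40, change the allocation text to 18 per group, and state that about 28 (14 per group) are expected after a 20% loss.

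In either case, describe the dropout as up to 20% rather than as a minimum, and drop the wording that the number could ensure the objectives. A statement of the precision that the chosen number gives for retention could take its place, but this is optional and would rest on an assumed retention rate.

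The cost is a short amendment. The stated number of completers becomes less favourable than a reader might have taken from the present text, and the resourcing statement has to be rechecked if 40 is kept, because at present it speaks only of 36.
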